# 7.1 Study Timeline

This 15-month single centre, randomised observational study is to be conducted in 3 phases:

- 1. Start-up period (3 months): to finalise and submit the REC form, to screen the CIED database for potential participants with high burden and/or episodes of AF.
- 2. Patient recruitment, ICM implant and data entry (9 months): during this period recruitment will take place and the confirm Rx will be implanted. Data entry to be completed within 6 weeks of enrolment and will be monitored every 2 months.
- 3. Completion of data entry and analysis (3 months): to finalise the data entry, adjudicate all electrograms and perform the statistical analysis. A final wrap up meeting will be convened at the end of the study with all key investigative staff contributing to the final report and manuscript.

## 7.2 Study Risks

The Confirm Rx™ ICM and the Reveal LINQ™ ICM implant procedure is safe and minimally invasive. They are both have CE marking and having been used in routine clinical practice for several years. The procedure will be performed under sterile conditions and local anaesthetic using the insertion tools supplied by the manufacturer. They have very similar implant techniques and they are both injected subcutaneously in the anterior chest wall.

There are no known contraindications. Potential adverse events include:

- bruising,
- haematoma (<1%),
- superficial infection (<1%),
- keloid formation,
- migration
- extrusion.

# 7.3 Study Benefits

Patient could get direct benefit from the study if the ICM is able to record arrhythmias that were not capture by the CIED. However, the main benefits from this study will be for future patients. It is important to understand how well the AF detection algorithms of these new generation ICM perform in comparison to the gold standard CIED. Furthermore, it will provide an opportunity to understand the pitfalls of the AF the current AF diagnostic algorithms and inform future optimisations.

# 8. PARTICIPANT IDENTIFICATION

## 8.1. Trial Participants

This trial is designed to include male and female adults with a dual-chamber CIED with a functioning atrial lead and Paroxysmal or Persistent Atrial Fibrillation.

## 8.2. Inclusion Criteria

The participant must satisfy the following conditions:

- Participant is willing and able to give informed consent for participation in the trial.
- Male or Female aged 18 years or above.
- History of paroxysmal and persistent AF
- Dual-chamber pacemaker, ICD or CRT device with a functioning atrial lead, able to record electrograms and remote monitoring.

## 8.3. Exclusion Criteria

The participant may not enter the trial if ANY of the following apply:

- Diagnosis of permanent AF.
- Contra-indications for implantable cardiac monitor.
- Unable to comply with the follow-up schedule.

## 8.4. Recruitment

Potential participants with a Cardiac Implanted Electronic Devices (Pacemakers, CRT and ICD) with a functioning atrial lead will be selected in Outpatient Pacemaker Clinics, Remote Pacemaker Clinics and hospital pacemaker database by the OUH NHS Trust Cardiac Rhythm Management Team. All members of the research team are part of the Cardiac Rhythm Management Care Team. Patients will be invited to participate in the study if there is presence of high AF burden or frequent AF episodes in a device download within the last year.

A letter of invitation, a patient information brochure and a consent form will be given to potential participants at the time of the Outpatient Clinic. In the Remote Pacemaker Clinic, as potential participants are not physically present, a letter of invitation and patient information brochure will be sent by post if they have non-permanent AF in their most recent transmission. Upon receiving and considering the information participants can use the contact the Arrhythmia Research Team by email or telephone to request more information or to express their interest in being enrolled.

If they wish to participate a baseline visit will be organised which will include informed consent, screening, and eligibility assessment.

## 8.5. Informed Consent

The participant must personally sign and date the latest approved version of the Informed Consent form before any trial specific procedures are performed.

Written and verbal versions of the Participant Information and Informed Consent will be presented to the participants detailing no less than: the exact nature of the trial; what it will involve for the participant; the implications and constraints of the protocol; the known side effects and any risks involved in taking part. It will be clearly stated that the participant is free to withdraw from the trial at

I

any time for any reason without prejudice to future care, without affecting their legal rights and with no obligation to give the reason for withdrawal.

The participant will be allowed as much time as wished to consider the information, and the opportunity to question the Investigator, their GP or other independent parties to decide whether they will participate in the trial. Written Informed Consent will then be obtained by means of participant dated signature and dated signature of the person who presented and obtained the Informed Consent. The person who obtained the consent must be suitably qualified and experienced and have been authorised to do so by the Chief/Principal Investigator. A copy of the signed Informed Consent will be given to the participant and another copy will be filed in the notes The original signed form will be retained at the trial site.

# 8.6 Screening and Eligibility Assessment

If a subject meets the inclusion criteria they will be invited to participate in the study. The inclusion criteria are based on the pacemaker interrogation performed in clinic.

After agreeing to participate and signing the consent form, the following data will be collected:

- 1. Demographics (age, gender, ethnicity)
- 2. Detailed collection of medical history which should include atrial fibrillation history, previous cardiac procedure (cardiac surgery, atrial fibrillation ablation, direct current cardioversion), significant co-morbidities
- 3. Imaging data recorded previously as part of standard clinical practice: left ventricular systolic function, diastolic function, evidence of valvular heart disease, cardiac chamber size.
- 4. Current medications
- 5. Height, weight and BMI
- 6. Current CIED name, model, implant indication

# 8.7 Randomisation

A block randomisation with block size of 2 will be used to assign each study subject with an ICM. There are two investigation arms in this study:

- Group A: Confirm Rx™
- Group B: Reveal LINQ™

As this study will enrol a total of 30 patients there will be 3 blocks of 10 patients each. In each block, subjects will be randomised to either Group A or Group B; therefore, at the end of each block there will be 5 subjects in each investigation arm. Randomisation will be performed during the baseline visit. A telephone call will be made to the research office and an envelope from the current block of 10 with the investigation of arm letter will be opened.

## 8.8 Blinding

Investigators and subjects will not be blinded to investigation arm.

At the end of follow-up, the CIED and ICM electrograms catalogued by the devices as AF will be adjudicated by two electrophysiologists blinded to patient data.

# 8.9 Baseline Assessments

Baseline assessment will include:

- 1. Detailed collection of medical history which should include atrial fibrillation history, previous cardiac procedure (cardiac surgery, atrial fibrillation ablation, direct current cardioversion), significant co-morbidities
- 2. Imaging data recorded previously as part of standard clinical practice: left ventricular systolic function, diastolic function, evidence of valvular heart disease, cardiac chamber size.
- 3. Current medications
- 4. Height, weight and BMI

# 8.9.1 Intervention – ICM implant (Confirm Rx™ or Reveal LINQ™)

The Confirm Rx™ ICM or Reveal LINQ™ ICM will be implanted as a Day Case. Prior to implant, recording of surface electrograms will be performed in V1 and V2 position to assess P and R-wave amplitudes. The procedure will be performed under sterile conditions and local anaesthetic (lidocaine 1%) using the insertion tools supplied by the manufacturer. They have very similar implant techniques and they are both injected subcutaneously in the anterior chest wall. If there is suboptimal R wave amplitude the operator can reposition the device. The subject will be premedicated with intravenous antibiotics as per Trust Policy to reduce the risk of infection. The operator may choose to close the wound with steri-strips, glue or a suture.

At the end of the procedure the R-wave amplitude will be recorded. Subjects will be taught how to use the mobile apps or the home-based monitor, depending on the device. They will be able to initiate recordings, send transmission and record their symptoms The CIED will be programmed to record any AT/AF and save the electrogram for future adjudication. The CIED and ILR date and time clocks will be synchronized.

The Confirm Rx™ ICM and the Reveal LINQ™ ICM implant procedure is safe and minimally invasive. There are no known contraindications. Potential adverse events include bruising, haematoma, superficial infection, keloid formation, migration or extrusion.

The LINQ™ and the Confirm Rx™ only transmit recordings to their company's servers (Carelink™, for Medronic; Merlin.net™, for Abbott) via their respective smartphone app or homebased monitor. ICM recordings can only be accessed on these servers by using the clinician web portal. The assigned trial specific ID number will be used to register the device in the Carelink (for Medtronic devices) and Merlin.net (for Abbott devices); thus, no identifiable patient information will be in the servers. Access to these servers is via the clinician web portal is password protected. Transmission reports will be downloaded from the Medtronic™ and Abbott™ servers and stored in password protect excel spreadsheet that will only be used in OUH trust computers.

## 8.10 Subsequent Visits

# 8.10.1 Scheduled Remote ICM and CIED Transmissions

Scheduled monthly remote ICM and CIED transmissions will be performed. Electrograms catalogued as AF episodes by the both devices will be downloaded for analysis from the clinicians web portal where the data is safely stored in Medtronic™ and Abbott™ server as it standard practice. All transmissions will be anonymous and only identified by the trial ID number.

If due to technical difficulties remote download is not possible subjects will be invited to attend Pacemaker Clinic for a download.

# 8.10.2 Visits

Visit 1: As is standard of care, Telephone Clinic review at 4-6 weeks after the ICM implant to review the wound, check performance and battery of ICM.

Visit 2: At 6 months, subjects will attend Device Clinic for a final download of both devices and at this time, they may choose to have the ICM removed. An updated drug history will be recorded.

# 8.11 Early Discontinuation/Withdrawal of Participants

During the course of the trial a participant may choose to withdraw early from the trial treatment at any time. This may happen for a number of reasons, including but not limited to:

- The occurrence of what the participant perceives as an intolerable AE.
- Inability to comply with trial procedures
- Participant decision
- Loss to follow-up

Participants may choose to withdraw from study assessments but may remain on study follow-up.

Participants may also withdraw their consent, meaning that they wish to withdraw from the study completely.

In addition, the Investigator may discontinue a participant from the trial treatment at any time if the Investigator considers it necessary for any reason including, but not limited to:

- Pregnancy
- Ineligibility (either arising during the trial or retrospectively having been overlooked at screening)
- Significant protocol deviation
- Significant non-compliance with treatment regimen or trial requirements
- Disease progression which requires discontinuation of the trial medication or results in inability to continue to comply with trial procedures

The type of withdrawal and reason for withdrawal will be recorded in the CRF.

In case of withdrawal from the study in an early stage (before intervention), the patient data will be excluded from the analysis and a new participant will be enrolled.

If the participant is withdrawn due to an adverse event, the Investigator will arrange for follow-up visits follow-up visits or telephone calls until the adverse event has resolved or stabilised.

If the participant withdraws, he may choose to:

- Continue to have the routine ICM (Confirm Rx™ or LINQ™) downloads as per clinical need
- To have the ICM (Confirm Rx™ or LINQ™)) turned off.
- Have the ICM (Confirm Rx™ or LINQ™)) removed. The investigators will organise an outpatient procedure.

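### Section 8.11 permits exclusion and replacement after the open-label allocation is known; opening the envelope in the implant session and reporting later withdrawals by arm is a cheap improvement

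*Combined protocol and SAP*

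**What the plan says.** Section 8.7 fixes the timing: "Randomisation will be performed during the baseline visit". A call is made to the research office and "an envelope from the current block of 10 with the investigation of arm letter will be opened". Section 8.8 adds that "Investigators and subjects will not be blinded to investigation arm"; only the two electrophysiologists who adjudicate electrograms are blinded, and they are blinded to patient data.

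The implant is a later step, a day-case procedure under 8.9.1. Training follows it: "Subjects will be taught how to use the mobile apps or the home-based monitor, depending on the device".

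Section 8.11 sets the rule for early withdrawal: "In case of withdrawal from the study in an early stage (before intervention), the patient data will be excluded from the analysis and a new" (that is, a replacement is recruited). The sentence just before that rule reads: "The type of withdrawal and reason for withdrawal will be recorded in the CRF".

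Section 8.7 also promises balance within blocks: "therefore, at the end of each block there will be 5 subjects in each investigation arm". Appendix B places screening, baseline (with randomisation) and implant all at Day 0. Section 11.2 names no analysis set.

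**The concern.** The rule in 8.11 draws its line at implant, but the allocation is known before that. It treats two different groups alike: people who leave before their envelope is opened, whose loss cannot depend on the arm, and people who leave afterwards, whose loss can. Only the first group can be dropped and replaced without touching the randomised comparison.

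Staff can also prompt such a loss. Section 8.11 lets the investigator discontinue a participant for any reason, including ineligibility overlooked at screening. The criteria in 8.2 and 8.3 do not ask for a smartphone or the ability to use one, so a practical obstacle might surface only once the device is known.

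At stake are the secondary objectives that compare the two ICMs on transmission success and on patient-activated recordings with symptoms. Both depend partly on how willing and able the patient is to use the technology. If reluctant users left one arm and were replaced by willing ones, that arm would look better than it should, and its count would show no gap.

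**Working it through.** **1. Order of events**

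| Step | Source | Arm known? | Withdrawal here is |
|---|---|---|---|
| Consent, baseline data | 8.6, 8.9 | No | excluded and replaced |
| Envelope opened at baseline visit | 8.7 | Yes from here | – |
| Interval up to implant, including the V1/V2 surface recordings | 8.9.1, Appendix B | Yes | excluded and replaced |
| After implant | 8.9.1 onward | Yes | not covered by this rule |

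The third row is the problem. Appendix B puts all of these steps at Day 0, so the interval is short, but it exists.

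**2. Which outcomes are exposed**

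The primary measures (sensitivity, specificity, PPV, NPV) set each ICM against the same patient's CIED. A patient without an ICM contributes nothing to them under any rule. The between-device comparisons of transmission and patient-activated recordings rely on the two groups being alike, so they carry most of the risk.

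**3. Share of an arm affected**

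The plan's figure is 30 patients, 15 per arm (Synopsis). The documents give no pre-implant withdrawal rate, so k withdrawals from one arm and none from the other are assumed, with replacement until 15 are implanted in each arm. Excluded share = k/(15 + k). The Fisher two-sided p compares k/(15 + k) with 0/15.

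| k | Randomised to the arm | Excluded share | Fisher p |
|---|---|---|---|
| 1 | 16 | 6.3% | 1.00 |
| 2 | 17 | 11.8% | 0.49 |
| 3 | 18 | 16.7% | 0.23 |
| 5 | 20 | 25.0% | 0.057 |

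A test of imbalance would not reliably expose a one-sided loss of this size. The counts by arm have to be shown.

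**4. Possible effect on transmission success (all rates assumed)**

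Let implanted patients transmit successfully at rate w, and let those who left have had rate x, with equal numbers of transmissions per patient. The rate for everyone randomised to the arm is (15w + kx)/(15 + k). The gap from the reported rate w is k/(15 + k) × (w − x).

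- w = 85%, x = 50%, k = 1: (12.75 + 0.50)/16 = 82.8%, gap 2.2 points.
- w = 85%, x = 50%, k = 3: (12.75 + 1.50)/18 = 79.2%, gap 5.8 points.
- w = 90%, k = 3, x = 80%, 50% or 0%: 88.3%, 83.3% or 75.0%, gaps of 1.7, 6.7 and 15.0 points.

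**5. What each part of a remedy would change**

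Take the case w = 85%, k = 3, with 15 allocated to the arm in all. Without replacement, 15 − 3 = 12 patients are implanted, still at 85%, so the reported figure is still 85%. Stopping replacement makes the loss visible but does not move the estimate, because people who were never implanted yield no ICM data. Only a later opening of the envelope can reduce selective loss itself.

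**6. How a replacement is allocated**

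Section 8.11 is silent. If the newcomer takes the next envelope, five per arm among implanted patients in each block of 10 is no longer assured. If the newcomer inherits the vacated slot, the arm is known before enrolment and concealment is lost for that patient. (Section 8.7 also gives the block size as both 2 and 10, which needs reconciling separately.)

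**The case against.** The strongest reply is that the risk is small and partly hypothetical. Four parts of it stand.

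- A reader might infer that these losses go unseen. They do not: 8.11 has the type and reason of withdrawal entered in the CRF. They leave the analysis, not the trial record. What is lacking is a requirement to report them by arm.
- A reader might infer that one arm is the app arm and the other is not. Section 12.3 says both devices transmit through their own smartphone apps, which the site already uses in place of home monitors, and section 5 says the current LINQ version can use an app. Section 8.9.1 does allow for an app or a home monitor according to device, so some difference in burden remains possible, but no passage reports a preference or a withdrawal pattern.
- All three steps are at Day 0, which leaves little time to act on the allocation.
- This is a 30-patient pilot. Section 11.2 specifies descriptive summaries and no between-arm test, and the 80% transmission figure in 5.1 is an expectation, not a decision threshold. Crossing 80% in an illustration shows no wrong decision.

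A reader might also infer that block balance is certainly lost. That depends on how replacements are allocated, which the documents do not say.

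The reply does not remove the stated rule, which still lets a patient be excluded and replaced after the arm is known to everyone involved. A short window and similar devices make this less likely; they do not justify the exclusion.

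**Conclusion.** The point holds as a design weakness that is cheap to correct. Sections 8.7, 8.8 and 8.11 together allow exclusion after randomisation with the arm known, and the replacement hides the gap in the analysed numbers. Each one-sided replacement is 6.3% of the patients randomised to an arm if there is one, and 16.7% if there are three. Under the assumed rates, three replacements shift an arm's transmission rate by between 1.7 and 15.0 points.

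These sizes rest on assumed withdrawal counts, assumed transmission rates, and replacement until 15 are implanted per arm. The documents do not show that such withdrawals will occur or that they differ by arm. They give no ground for saying that the primary accuracy estimates against the CIED are seriously affected, or that the sample-size figures of 327 episodes and 8 subjects per ICM change. The gain from a correction comes from the later opening of the envelope and from accounting by arm, and falls mainly on the between-device secondary comparisons.

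**What to change.** **Section 8.7 and Appendix B.** Move randomisation from the Baseline column to the Implant column. Open the envelope in the Day 0 implant session, as late as is practical before implant: after consent and baseline data, and after the V1/V2 surface recordings unless that mapping is device-specific, which the documents do not settle.

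**Section 8.11.** Limit exclusion and replacement to participants who withdraw before their envelope is opened. Anyone who withdraws later is reported under the allocated arm with the reason, and their slot is not reused.

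**Section 11.2.** State that the device analyses cover patients who were randomised and implanted, and show the numbers randomised and implanted by arm beside them.

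**Cost.** A few sentences and one moved tick; no extra visit, since baseline and implant are both Day 0. Both devices must be to hand at every implant session. Slightly fewer than 30 may be implanted. The plan's own minimum is 8 per ICM, from 327/(7 × 6) = 7.8, so 15 per arm leaves room on that reckoning. That minimum credits every subject with 7 episodes a month; if only the 40% in 11.1 had episodes, it would be 7.8/0.4 = 19.5, so the margin should not be leaned on heavily.

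If enrolment is already complete, the timing cannot be changed, but the by-arm account can still be compiled from the CRF.

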# 8.12 Definition of end of study

The end of the study will be the date of the last 6 month Confirm Rx™ ICM or LINQ™ ICM and CIED report download.

# 9 TRIAL INTERVENTIONS

# 9.1 Other Interventions

No other interventions will be performed except for the ICM implant and, at the end of the trial, if the subject wishes, ICM explant (see 8.9.1)

# **10 SAFETY REPORTING**

# **10.1** Definition of Serious Adverse Events

A serious adverse event is any untoward medical occurrence that:

- results in death
- is life-threatening
- requires inpatient hospitalisation or prolongation of existing hospitalisation
- results in persistent or significant disability/incapacity
- consists of a congenital anomaly or birth defect.

Other 'important medical events' may also be considered a serious adverse event when, based upon appropriate medical judgement, the event may jeopardise the participant and may require medical or surgical intervention to prevent one of the outcomes listed above.

NOTE: The term "life-threatening" in the definition of "serious" refers to an event in which the participant was at risk of death at the time of the event; it does not refer to an event which hypothetically might have caused death if it were more severe.

# **10.2** Reporting Procedures for Serious Adverse Events

A serious adverse event (SAE) occurring to a participant should be reported to the REC that gave a favourable opinion of the study where in the opinion of the Chief Investigator the event was 'related' (resulted from administration of any of the research procedures) and 'unexpected' in relation to those

procedures. Reports of related and unexpected SAEs should be submitted within 15 working days of the Chief Investigator becoming aware of the event, using the HRA report of serious adverse event form.

